6.3. Other Endpoints

6.3.1. GMTs and GMFRs

RSV A NTs, RSV B NTs, and RSV A/B NTs at Visit 101 and Visit A102 will be summarized with n, GMTs, and 95% CIs for Groups 1, 2, 4, 6, and 7. The fold rise of RSV A NTs, RSV B NTs, and RSV A/B NTs at Visit A102 will be summarized with n, GMFR, and the 95% CI for Groups 1, 2, 4, 6, and 7.

QIV strain-specific HAI titers at Visit 101 and Visit A102 will be summarized with n, GMTs, and 95% CIs for Groups 1, 5, and 7. The fold rise of QIV strain-specific HAI titers at Visit A102 will be summarized with n, GMFR, and the 95% CI for Groups 1, 5, and 7.

SARS-CoV-2 strain-specific NTs at Visit 101 and Visit A102 will be descriptively summarized with n, GMTs, and 2-sided 95% CIs for Groups 1, 2, 3, 6, and 7. The fold rise of SARS-CoV-2 strain-specific NTs at Visit 102 will be descriptively summarized with n, GMFRs, and 2-sided 95% CIs for Groups 1, 2, 3, 6, and 7.

6.3.2. HAI Seroprotection and HAI Seroconversion

Descriptive statistics, including the proportion (%) of participants with HAI seroprotection at Visit A101 and A102, HAI seroconversion at Visit A102, the numerator (n) and the denominator (N) used in the proportion calculation, and the 95% CI for percentage using the Clopper-Pearson method, will be presented for each strain in Groups 1, 5, and 7 in the evaluable immunogenicity population.

6.3.3. SARS-CoV-2 NT Seroresponse

Descriptive statistics, including the proportion (%) of participants with SARS-CoV-2 strain-specific NT seroresponse at Visit A102, the numerator (n) and the denominator (N) used in the proportion calculation, and the 95% CI for percentage using the Clopper-Pearson method, will be presented for each strain in Groups 1, 2, 3, 6, and 7 in the evaluable immunogenicity population.

6.3.4. RSV NT Seroresponse

Descriptive statistics, including the proportion (%) of participants with RSV A NT seroresponse and RSV B NT seroresponse at Visit A102, the numerator (n) and the denominator (N) used in the proportion calculation, and the 95% CI for percentage using the Clopper-Pearson method, will be presented for each strain in Groups 1, 2, 4, 6, and 7 in the evaluable immunogenicity population.

6.3.5. Additional Analysis

6.3.5.1. Descriptive Between-Group Comparisons

GMRs on RSV A NTs, RSV B NTs, and SARS-CoV-2 strain-specific NTs will be descriptively compared between Group 1 and Group 2 to explore potential coadministration of QIV interference to the combination vaccine immune response.

GMRs on RSV A NTs, RSV B NTs, and SARS-CoV-2 strain-specific NTs will be descriptively compared between Group 7 and Group 6 to explore immune response from coadministration of RSVpreF with BNT162b2, with or without QIV coadministration.

GMRs on RSV A NTs, RSV B NTs, and SARS-CoV-2 strain-specific NTs will be descriptively compared between Group 2 and Group 6 to explore immune response differences between the combination vaccine (1 injection) and coadministration of RSVpreF with BNT162b2.

GMRs on RSV A NTs, RSV B NTs, QIV strain-specific HAI titers, and SARS-CoV-2 strain-specific NTs will be descriptively compared between Group 1 and Group 7 to explore immune response differences.

All of these descriptive comparisons of GMRs will be summarized with 95% CIs.

6.3.5.2. Sensitivity Analysis

RSV A NTs and RSV B NTs at Visit A102 will be summarized with n, GMTs, and 95% CIs for Groups 1, 2, 6, 7, and 4. Using Group 4 as reference, GMR will be summarized with 95% CI. Model-adjusted LS GMTs and LS GMRs (to Group 4) with associated 95% CIs will be based on data from all 5 groups using the ANCOVA model ([Section 5.2.2.5](#)).

SARS-CoV-2 strain-specific NTs at Visit A102 will be summarized with n, GMTs, and 95% CIs for Groups 1, 2, 6, 7, and 3. Using Group 3 as reference, GMR will be summarized with 95% CI. Model-adjusted LS GMTs and LS GMRs (to Group 3) with associated 95% CIs will be based on data from all 5 groups using the ANCOVA model ([Section 5.2.2.5](#)).

QIV strain-specific HAIs at Visit A102 will be summarized with n, GMTs, and 95% CIs for Groups 1, 7, and 5. Using Group 5 as reference, GMR will be summarized with 95% CI. Model-adjusted LS GMTs and LS GMRs (to Group 5) with associated 95% CIs will be based on data from all 3 groups using the ANCOVA model ([Section 5.2.2.5](#)).

6.3.5.3. Combined Group 1 and Group 2 Analysis

If both primary objectives are achieved ($LBCI > 0.5$) but the lower bound is < 0.667 , Group 1 and Group 2 will be combined to assess combination vaccine [RSVpreF+BNT162b2] immune response. In this analysis, the combined group will be compared with Groups 3 and 4 for the following:

- 95% CI for the GMT ratio (GMT combination/GMT RSVpreF alone) for RSV subgroup A and RSV subgroup B
- 95% CI for the GMT ratio (GMT combination/GMT bivalent BNT162b2 alone) for each COVID-19 strain
- 95% CI for the difference in proportions (combination minus RSVpreF alone) of participants achieving seroresponse for RSV subgroup A and RSV subgroup B
- 95% CI for the difference in proportions (combination minus bivalent BNT162b2 alone) of participants achieving seroresponse

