		
2. Updated immunogenicity analysis based on CBER feedback to RSV studies and the clinical development plan on combined vaccine.
 
3. Clarified the derivation for cases of myocarditis or pericarditis.
 
4. Updated the meaning of “N-binding antibody” at baseline.
 
5. Typo correction.
	
2. Added seroresponse for RSV A and RSV B in Section 3.3.6 and its analysis in Section 6.3.4. Added a descriptive immunogenicity analysis for combining Groups 1 and 2 in Section 6.3.5.3.
 
3. Updated Section 3.5.3.
 
4. Updated Section 3.4.2.
 
5. Changed “GMR of NTs” to “GMR of HAI titers” in the secondary immunogenicity objective on QIV (Group 7 versus Group 5) in the Section 2.2 table, and changed “these assessment” to “these assessments” in Section 3.5.3.

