5.1.5. Multiplicity Adjustment

Type I error of 5% is equally split between the 2 primary immunogenicity objectives (2-sided 2.5% for each). The first primary immunogenicity objective will be achieved if all 8 null hypotheses are rejected. The second primary immunogenicity objective will be achieved if all 4 null hypotheses are rejected. The study is considered successful if either primary immunogenicity objective is achieved.

The secondary immunogenicity objectives will be tested sequentially after the primary objective(s) is achieved as described in the schema below.

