6.1.2. Primary Immunogenicity Endpoints for Combined Vaccine (Group 2) Noninferiority Objective

6.1.2.1. Main Analysis

- Estimand strategy: Hypothetical approach ([Section 2.2.1.1](#)).
- Analysis set: Evaluable immunogenicity population ([Section 4](#)).
- Analysis timing: Final analysis of immunogenicity objective.
- Intercurrent events and missing data: All data collected after or at intercurrent events will not be included ([Section 2.2.1.1](#)); missing data will not be imputed ([Section 5.3.2](#)).
- Analysis methodology: GMR, defined as the ratio of all of the 4 strain/subgroup-specific serology results measured by RSV NT and SARS-CoV-2 NT GMTs in Group 2 to that in single vaccine administered alone (eg, Groups 3 and 4) at Visit A102 will be summarized along with the 97.5% CI ([Section 5.2.2.3](#)). Descriptive statistics, including sample size (n), and GMTs at Visit A102 will be presented for Group 2 and Groups 3 and 4 ([Section 5.2.2](#)).
- RCDCs for each of the 4 strain/subgroup-specific serology results at Visit A102 measured by RSV NT and SARS-CoV-2 NT will be plotted after vaccination for the applicable groups (eg, RSV A NT for Group 2 vs Group 4).

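### Does the loosely worded 0.667 trigger for the pooled Group 1 and Group 2 analysis need to be tightened?

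*SAP*

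**What the plan says.** SAP 6.3.5.3 sets two conditions for combining Groups 1 and 2. The first is "If both primary objectives are achieved", with the 0.5 criterion for the lower confidence bound given in brackets. The second follows at once: "but the lower bound is < 0.667". The combined group is then compared with Group 3 and Group 4 by GMT ratio and by difference in seroresponse for RSV A, RSV B and the COVID-19 strains, each with a 95% CI.

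SAP 5.1.5 defines the first condition exactly: "The first primary immunogenicity objective will be achieved if all 8 null hypotheses are rejected", and "The second primary immunogenicity objective will be achieved if all 4 null hypotheses are rejected". The primary GMRs are reported at the 97.5% level (SAP 6.1.1.1 and 6.1.2.1; for Group 2, "at Visit A102 will be summarized along with the 97.5% CI"). The sensitivity section, SAP 6.3.5.2, shows the same ratios at 95%, for example "Using Group 3 as reference, GMR will be summarized with 95% CI".

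The SAP version history records the origin and status of the pooled analysis: "Added a descriptive immunogenicity analysis for combining Groups 1 and 2 in Section 6.3.5.3". It places this under immunogenicity updates made on CBER feedback and the clinical development plan for the combined vaccine.

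**The concern.** The second condition speaks of one lower bound where there are twelve: eight for Group 1 and four for Group 2. Four of the Group 1 bounds are HAI bounds, and the pooled analysis contains no influenza antigen. The text gives no rule for any versus all, or for one group versus both. It does not repeat the confidence level, and it does not explain 0.667.

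The trigger can be evaluated only once the primary bounds are known. A rule left open would therefore be settled with the results in view, and the choice decides whether the pooled tables appear. Pooling also averages recipients with and without QIV. If that average were used to support a claim, it could soften a signal of interference in Group 1.

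**Working it through.** **Inputs.** Protocol Table 5: 135 evaluable per group, true GMR 1, margin 2-fold, 1-sided alpha 0.0125, SDs on the natural-log scale of 1.1 (RSV A, RSV B, H1N1, H3N2), 1.5 (BA.4/BA.5), 1.3 (reference strain) and 1.2 (both B strains). The correlation between antigens is not in the documents and is assumed below.

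**The plan's own figures.** Power for a two-sample t test with 268 degrees of freedom comes out at 99.8% (SD 1.1), 99.3% (1.2), 98.3% (1.3) and 93.8% (1.5), as in Table 5. Multiplying the rounded values:

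- four tests: 0.998² × 0.938 × 0.983 = 0.918
- eight tests: 0.918 × 0.998² × 0.993² = 0.902

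Both agree with the stated 91.8% and 90.2%.

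**Lower bounds when every observed GMR is 1.0.** LB = exp(−t × SD × √(2/135)), with √(2/135) = 0.1217, t = 2.254 at 97.5% and t = 1.969 at 95%.

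| Antigen | SD | LB at 97.5% | LB at 95% |
|---|---|---|---|
| RSV A, RSV B, H1N1, H3N2 | 1.1 | 0.739 | 0.768 |
| B strains | 1.2 | 0.719 | 0.750 |
| Reference strain | 1.3 | 0.700 | 0.732 |
| BA.4/BA.5 | 1.5 | 0.663 | 0.698 |

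At 97.5% only BA.4/BA.5 is below 0.667, so an any-bound rule fires and an all-bounds rule does not. At 95% nothing is below. For BA.4/BA.5 the two levels disagree for observed GMRs from 0.667/0.698 = 0.956 to 0.667/0.6626 = 1.007.

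**What the text settles.**

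- *Level.* The phrase about the lower bound comes directly after the bracketed 0.5 criterion, so it refers to the bound that decides the primaries. That is the 97.5% bound. The 95% ratios in SAP 6.3.5.2 are a sensitivity display on which no success is judged.
- *Antigens pooled.* SAP 6.3.5.3 lists its RSV and COVID-19 outputs without an antigen condition. Once triggered, all four antigens are pooled.
- *HAI bounds.* The pooled group is compared only with Groups 3 and 4, and Group 2 has no HAI testing. An influenza bound has no bearing on the purpose of the analysis.

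**What stays open.** Any or all of the eight RSV and SARS-CoV-2 bounds, and one group or both. Simulations of Groups 1 to 5 with shared controls (40,000 to 300,000 trials per setting, true GMR 1, 97.5% level) give the share of trials meeting both primaries in which pooling is triggered:

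| Reading | Correlation 0 | 0.5 | 0.8 |
|---|---|---|---|
| Any of the 8 RSV/SARS-CoV-2 bounds | 93% | 84% | 78% |
| At least one bound in each group (HAI counted in Group 1) | 75% | 55% | not run |
| Same antigen low in both groups | 54% | not run | 39% |
| All 8 bounds | about 0.1% | not run | about 1% |

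An all-bounds rule would almost never fire, so it would empty the section of content. An analyst looking for a workable meaning arrives at any relevant bound.

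**What depends on the choice.** For each antigen, ln(pooled GMT) = (n₁ ln GMT₁ + n₂ ln GMT₂)/(n₁ + n₂). The n, GMT and 95% CI for each group are reported regardless (SAP 6.3.1 and 6.3.5.2), and each CI gives back the group's SD. The seroresponse counts and denominators are reported regardless too (SAP 6.3.3 and 6.3.4). A reader can rebuild the pooled comparison from tables that always exist.

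**The case for a change.** The best argument for a change is that a conditional analysis is prespecified only if its condition can be evaluated without judgement. This one fails that test at the design assumptions themselves, and the remedy is short: name the bounds, or drop the 0.667 condition. The pooling point adds to it. With equal group sizes, assumed GMRs of 0.70 in Group 1 and 1.0 in Group 2 give a pooled √(0.70 × 1.0) = 0.84.

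Part of this stands. The any-or-all and one-or-both questions are not answered anywhere in the two documents, and the SAP gives no reason for 0.667.

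The consequence does not follow. Selective reporting matters when the selected result can support a claim. Here both primaries must already have been met, the hypotheses in SAP 5.1.1 to 5.1.4 involve no pooled group, SAP 7.1.1 spends all type I error at the primary analysis, and the version history calls the analysis descriptive. The averaging cannot hide interference either. The Group 1 and Group 2 ratios stand separately in the primary tables, and SAP 6.3.5.1 compares the two groups directly "to explore potential coadministration of QIV interference to the combination vaccine immune response". Dropping the threshold would also remove a feature added among updates attributed to CBER feedback and the development plan, neither of which is available here.

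**Conclusion.** No change is called for. The wording is incomplete on one point: any or all bounds, one group or both. The analysts can fill it sensibly by taking any 97.5% lower bound for RSV A, RSV B, BA.4/BA.5 or the reference strain in either group. Under that reading the table is produced in most eligible trials: 93%, 84% and 78% at assumed correlations of 0, 0.5 and 0.8, with true GMR 1, Table 5 SDs and 135 per group.

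Under every reading the primary and secondary conclusions, the alpha, the sample size and the separate Group 1, Group 2 and Group 1 to Group 2 results are the same. The difference is whether one supporting descriptive table is printed, and its content can be rebuilt from tables that are always reported. The percentages depend on the assumed correlations and would shift with a true GMR other than 1; the conclusion does not depend on them.

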6.4. Subset Analyses

No subset analysis is planned.

6.5. Baseline and Other Summaries and Analyses

For each vaccine group (Group 1 to 7), descriptive summary statistics for demographic characteristics (age at vaccination, sex, race, ethnicity, height, weight, and BMI) and prior exposure to SARS-CoV-2 measured by the N-binding assay will be generated, as well as for all participants in total, based on the safety population. Summary data will also be presented for the evaluable immunogenicity population.

6.5.1. Study Conduct and Participant Disposition

The number and proportion of randomized participants will be included in the participant disposition summary. In addition, vaccinated participants who completed the study, and participants who withdrew after vaccination, along with the reasons for withdrawal, will be tabulated by vaccine group and for all participants.

Participants excluded from the evaluable and mITT populations will also be summarized with reasons for exclusion.

The e-diary completion rate will be summarized for the safety population, by vaccine group, as well as summarized with the categorized days specified in [Section 3.4.3](#).

Standard listings will be generated, including, but not limited to, participants who withdrew during the study, participants excluded from analysis populations, and participants with important protocol violations.

6.6. Safety Summaries and Analyses

6.6.1. Adverse Events

For all of the AEs categorized in [Section 3.1.2.3](#), each individual AE will be categorized by MedDRA and descriptively summarized by vaccine group.

AEs are classified into 1 of 3 tiers ([Section 3.5.1](#)). For Tier 1 events, 2-sided 95% CIs for the difference between the comparator group and reference group in the percentage of participants reporting the events, based on the Miettinen and Nurminen³ method, will be provided. In addition, the asymptotic p-values will also be presented for the difference between groups in the percentage of participants reporting the events, based on the same test statistic and under the assumption that the test statistic is asymptotically normally distributed. AE displays will be sorted in descending order of point estimates of risk difference within the SOC. The analysis on Tier 1 events is planned for comparing Groups 4, 6, and 7 pooled (RSVpreF coadministered or administered alone) and Groups 1, 2, 4, 6, and 7 pooled (RSVpreF combination or coadministered or administered alone), to Groups 3 and 5 pooled (Bivalent BNT162b2 or QIV administered alone, reference group).

It should be recognized that most studies are not designed to reliably demonstrate a causal relationship between the use of a pharmaceutical product and an AE or a group of AEs. Except for select events in unique situations, studies do not employ formal adjudication procedures for the purpose of event classification. As such, safety analysis is generally considered an exploratory analysis and its purpose is to generate hypotheses for further investigation. The 3-tier approach facilitates this exploratory analysis.

6.6.2. Myocarditis or Pericarditis

The variable derived in [Section 3.5.3](#) will be summarized with count, percentage, and 95% CI for each vaccine group.

A listing for ECG and measurement of troponin for potential myocarditis/pericarditis evaluation will be provided. Symptoms, ECG, troponin level, cardiac study results, cardiac function evaluation, and final diagnosis results will all be listed for any participants with onset of signs and symptoms within 28 days after vaccination.

7. INTERIM ANALYSES

7.1. Introduction

7.1.1. Analysis Timing

No formal interim analysis will be conducted for this study phase.

The primary analysis will be performed on safety and immunogenicity data through 1-month postvaccination visit (ie, Visit A102); all type I error will be spent at this analysis. Once this analysis has been completed, study participants and the study team may be unblinded to study intervention allocation. The 6-month safety data will be summarized when they become available.

7.1.2. Blinding and Unblinding

As described in [Section 3.1.1](#), an unblinded statistician will send the barcode listings to sample management for specific assay testing.

